## 5.6 Duration of Therapy

Duration of therapy will depend on individual response, evidence of disease progression and tolerance. In the absence of treatment delays due to adverse events, patients may continue on treatment until one of the following criteria applies:

- Disease progression (for regorafenib or TAS-102 arm in Phase II), see below \* regarding SGI-110 + irinotecan cohort.
- Intercurrent illness that prevents further administration of treatment,
- Unacceptable adverse event(s),

CONFIDENTIAL

This document is confidential. Do not disclose or use except as authorized.

- Participant demonstrates an inability or unwillingness to comply with the medication regimen and/or documentation requirements
- Participant decides to withdraw from the study, or
- General or specific changes in the participant's condition render the participant unacceptable for further treatment in the opinion of the treating investigator.

\*In both Stage 1 and Stage 2, subjects receiving SGI-110 + irinotecan may continue receiving their assigned treatment if their disease progresses based on RECIST criteria if 1) the patient is clinically stable, 2) the patient is informed of their scan results and agrees to continue therapy, and 3) the patient's provider agrees that remaining on study would be appropriate for the patient.

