**Arm B - Regorafenib**

	Pre-Study	C1 d1	C1 d8	C1 d15	C1 d22	C2 d1	C2 d8	C2 d15	C2 d22	C3 d1 a	C3 d8 a	C3 d15 a	C3 d22 a	Off Study b
Regorafenib c		X -----				X -----				X -----				
Informed consent	X													
History	X													
QoL questionnaire		X								X d				X
Concurrent meds	X	X		X		X		X		X				X
Physical exam (Ht, Wt, BSA, VS) e	X	X				X				X				X
Performance Status	X	X				X				X				X
Blood Pressure f		X	X	X	X	X	X							
CBC w/diff, plts	X	X		X		X		X		X				X
Serum chemistry g	X	X		X		X		X		X				X
Lipase		X												
CEA	X	X				X				X				X
Urinalysis	X													X
ECG	X													
Adverse event evaluation		X-----X												X
Tumor measurements	X	Repeated every 8 weeks. Documentation (radiologic) must be provided for subjects removed from study for progressive disease.												X b
Radiologic evaluation	X	Radiologic measurements should be performed every 8 weeks												X b
Archival Tissue	X													
B-HCG	X h													
Research Bloods		X		X		X		X		X				X

a: All study calendar evaluations for cycle 3 are representative of cycle 3 and beyond.  
b: Off-study evaluation should be performed within 30 days of last dose.  
c: Arm B (regorafenib 160 mg/day days 1-21). Treatment cycle is 28 days  
d: QoL surveys will be done on C3D1 and every other cycle subsequently (i.e. Cycle 5 Day 1, Cycle 7 Day 1, etc)  
e: Baseline height will be measured and recorded once pre-study, and this value for height will be used through the patient's duration of study  
f: Weekly blood pressures for first 6 weeks (can be checked with primary care physician or at patient's home), further blood pressure monitoring as determined by history of abnormality  
g: Albumin, alkaline phosphatase, total bilirubin, BUN, calcium, chloride, glucose, phosphorus, potassium, total protein, SGOT [AST], SGPT [ALT], sodium.  
h: Serum pregnancy test (women of childbearing potential).

CONFIDENTIAL

This document is confidential. Do not disclose or use except as authorized.

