**Quality of Life Assessment:** Quality of life will be assessed with the Functional Assessment of Cancer Therapy (FACT-C) quality of life tool. An overall quality of life score for the domains: physical well-being, social/family well-being, emotional well-being, and functional well-being, as well as the colon cancer specific subscale score will be obtained at the start of the study (Cycle 1 Day 1), at the beginning of cycle three (Cycle 3 Day 1), every other cycle subsequently (i.e. Cycle 5 Day 1, Cycle 7 Day 1, etc), and at the off study visit for every patient. Scoring will follow guidelines provided by FACIT administration guidelines manual. The change in total score between pre-treatment and the start of cycle three will be compared between arms of the study with a t-test. Two subscale sums of the total score: the sum of physical and functional well-being,

CONFIDENTIAL

This document is confidential. Do not disclose or use except as authorized.

and the sum of social/family and emotional well-being, will be similarly analyzed. The change in the colon cancer specific domain will also be compared between arms of the study. We anticipate that we will have minimal missing data at the start of cycle 3 as this is the first time a patient could come off study for progression. At this time point, any missing data would be due to DLTs, SAE events, or voluntary withdrawal. In these cases, documentation of the reason for missing data and the QoL at the time of withdrawal will be obtained with the off study evaluation.

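### The FACT-C comparison at Cycle 3 Day 1 ignores the baseline score and randomisation factors, and its list of causes of missing forms omits progression and non-serious deterioration

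*Combined protocol and SAP*

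**What the plan says.** Section 14.1, Quality of Life Assessment, sets the analysis: "The change in total score between pre-treatment and the start of cycle three will be compared between arms of the study with a t-test". The two subscale sums are handled in the same way, and the colon cancer domain is also compared between arms. No covariate, missing-data rule or sensitivity analysis is named.

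On missing forms, the same paragraph expects "minimal missing data at the start of cycle 3 as this is the first time a patient could come off study for progression". It continues: "At this time point, any missing data would be due to DLTs, SAE events, or voluntary withdrawal". It then adds: "In these cases, documentation of the reason for missing data and the QoL at the time of withdrawal will be obtained".

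Other parts of the protocol bear on this:

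- **Timing.** In the Arm B regorafenib calendar (section 9), "Radiologic measurements should be performed every 8 weeks" and "QoL surveys will be done on C3D1 and every other cycle subsequently". The Arm A and TAS-102 calendars have the same schedule.
- **Stopping.** Section 5.6 lists "Disease progression (for regorafenib or TAS-102 arm in Phase II" among the reasons to stop. It lets Arm A patients continue after RECIST progression under three conditions. It also lets treatment stop when changes in the patient's "condition render the participant unacceptable for further treatment in the opinion of the treating investigator".
- **Deterioration without a scan.** Section 10.1.4.3 has a category for symptomatic deterioration without objective progression. Section 10.1.6 counts clinical deterioration attributed to disease as a PFS event.
- **Off-study form.** Section 5.9, section 14.1 and all three phase II calendars ask for FACT-C at discontinuation or off study. Section 10.2 makes it optional.
- **Randomisation.** Sections 4.3 and 14.1 (Stratification Factors) name two factors: the standard treatment, and time from last irinotecan.

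**The concern.** There are two separate matters.

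The first is precision. Baseline FACT-C is collected at Cycle 1 Day 1 and allocation is stratified, yet the test uses only the raw change. With 32 control patients at most, a wider interval than necessary is a real, if modest, loss.

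The second is interpretation. The reason given for expecting few missing forms is that progression cannot take a patient off study before Cycle 3 Day 1. That does not protect the Cycle 3 Day 1 form itself, because the first scheduled scan falls at that visit. It also does not cover deterioration before the visit that is neither a DLT, nor serious, nor the patient's own decision. Because the arms have different rules at progression, loss may differ by arm. If it does, and no rule says how off-study forms are used, a reader could not tell whether the reported difference was affected.

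**Working it through.** **No quality-of-life figure to reproduce.** The plan gives no SD, power, alpha or expected missing rate for FACT-C. The values of r, d and f below are therefore assumptions, shown as ranges. All results are in SD units of the score.

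**1. Do the scan and the form coincide?** Two 28-day cycles are 56 days, or 8 weeks. The first 8-week scan therefore falls at about Cycle 3 Day 1.

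**2. Is the list of causes complete?** Deaths and events needing admission are SAEs (11.1.2), so the list covers them. Progression on the week-8 scan (5.6) and non-serious deterioration (5.6, 10.1.4.3, 10.1.6) are not on it. Section 10.1.1 also allows for objective progression before the end of cycle 1.

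**3. Precision with complete data (64 and 32).** With correlation r between baseline and follow-up, and t = 1.986 on 94 df:

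- √(1/64 + 1/32) = 0.2165.
- Change score: half-width = t × √(2(1−r)) × 0.2165. This is 0.471 at r = 0.4 and 0.333 at r = 0.7.
- ANCOVA on baseline: half-width = t × √(1−r²) × 0.2165. This is 0.394 at r = 0.4 and 0.307 at r = 0.7.
- By formula the interval is 16% narrower (0.394/0.471) or 8% narrower (0.307/0.333).
- Adding two factors with no effect costs a little. In 4,000 simulated trials the mean half-widths were about 0.47 against 0.40 (r = 0.4) and 0.33 against 0.31 (r = 0.7), or about 15% and 6% narrower.

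**4. How many patients could be involved?** PFS events by week 8 are an upper guide only. Many such patients will still complete a form. Two curves are used because the printed hazards do not give the stated control median. Cumulative hazard at week 12 is 6 × 0.0113 + 6 × 0.0558 = 0.4026, so the median is 12 + (0.6931 − 0.4026)/0.3238 = 12.9 weeks, about 3.0 months rather than 1.9.

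- Stated median, exponential: 1.9 months = 8.26 weeks. S_B(8) = 0.5^(8/8.26) = 0.511 and S_A(8) = 0.511^0.526 = about 0.70. Events: about 16 of 32 (Arm B) and 19 of 64 (Arm A).
- Printed hazards, first rate applied from week 0: S_B(8) = exp(−(6 × 0.0113 + 2 × 0.0558)) = 0.836 and S_A(8) = 0.836^0.526 = 0.910. Events: about 5 of 32 and 6 of 64.

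**5. Illustrative shift in the A-minus-B difference.** Let q be the share with an event and f the share of those patients without a form. Assume they change d = 0.5 SD worse than the others. The mean among forms received rises by d·q·f·(1−q)/(1−q·f) in each arm.

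| f in Arm B | f in Arm A | Stated medians | Printed hazards |
|---|---|---|---|
| 1 | 0 | −0.244 | −0.082 |
| 1 | 1 | −0.096 | −0.037 |
| 0.5 | 0.5 | −0.021 | −0.016 |
| 0.5 | 1 | +0.066 | +0.008 |
| 0 | 1 | +0.149 | +0.045 |

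For the top left cell: 0.5 × 0.489 × 0.511/(1 − 0.489) = 0.244 in Arm B and 0 in Arm A. About 64 and 16 forms would then remain, and the t-test half-width would be 0.43 (r = 0.7) to 0.61 (r = 0.4). Even the largest shift is below the smallest complete-data half-width, 0.307.

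**The case against.** **The t-test is valid.** This stands. Under randomisation with complete data it is unbiased. A reader might infer that an unadjusted test gives a wrong answer, but nothing in the documents supports that. The cost is precision only, and it shrinks as the correlation rises.

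**The omission of progression is reasoned.** In part. Scheduled detection does fall at Cycle 3 Day 1 and not before it. The reasoning fails at that visit and for earlier deterioration or unscheduled progression, whose frequency the documents do not give.

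**The safeguards are largely there already.** This stands and limits the point. Section 5.9 requires the reason and date of removal for every criterion in 5.6, so a reading that reasons are collected only for the causes listed in 14.1 would be wrong. An Arm B patient stopped on the week-8 scan is due a form at about the right time. Section 10.2 is the only outlier on whether the form is required. What is absent is a rule for using it.

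**Bias in a known direction.** A reader might take the event counts as missing-form rates and conclude that the comparison favours Arm B. The documents do not support this. Forms are requested from patients who stop, Arm A toxicity can also remove forms, and the sign changes across the table. The −0.24 SD value needs every Arm B event patient and no Arm A event patient to lose the form.

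**The comparator factor may not be recorded for Arm A.** Section 4.3 describes the choice of drug for treatment-naive patients only in the standard arm. But a factor that stratifies randomisation has to be fixed beforehand, and adjustment for baseline stands without it.

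**Conclusion.** The point holds as a modest improvement to a supportive analysis. The unadjusted test gives up about 6 to 15% of interval width, if the baseline correlation is 0.7 to 0.4. The list of causes of missing forms is incomplete against sections 5.6, 10.1.4.3 and 10.1.6, the status of the off-study form is contradictory, and its use is undefined. Unequal loss by arm is possible. Its direction is unknown, and under the assumed 0.5 SD deficit the shift ranges from −0.24 to +0.15 SD on the stated medians, or −0.08 to +0.05 SD on the printed hazards, all below sampling error.

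A reader might infer that this touches the trial's main result. It does not: FACT-C is not a listed phase II objective in 1.3 or 14.1, carries no alpha, and leaves the PFS conclusion unaffected.

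**What to change.** 1. In 14.1, replace the t-test with ANCOVA of the Cycle 3 Day 1 score on arm, baseline score and the two randomisation factors as recorded at randomisation. Use it for the total score, both subscale sums and the colon cancer domain.
2. Delete the word optional for the off-study form in 10.2. Add progression and non-serious clinical deterioration to the causes in 14.1.
3. Count a discontinuation form completed at the week-8/Cycle 3 Day 1 visit as the Cycle 3 Day 1 form. Use earlier discontinuation forms in a sensitivity analysis only, and only if completed before any crossover treatment. The restriction matters because crossover may begin 14 days after the last dose (5.8), while the off-study visit may fall up to 30 days after it (5.9).
4. Tabulate missing forms by arm and reason, using the removal reasons already recorded under 5.9, with deaths listed separately.

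Two additions are optional: a sensitivity analysis that shifts missing scores by an assumed amount in each arm, and completion of the form before the scan result is discussed. The second changes visit conduct and is not needed for the fix.

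The cost is analysis wording, one word in 10.2 and slightly more analysis, with no new form or visit. Patients who stop before week 8 will still have no week-8 score. ANCOVA assumes that missing forms depend only on arm, baseline and the two factors, so items 3 and 4 are needed beside it.

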#### **4.3 Patient assignment and randomization procedure for second cohort**

Each subject who satisfies the eligibility criteria and is accepted for the study will be assigned a unique identification number. The subject number will be used to identify the subject throughout the study and will be entered on all study documents. Once the subject identification number has been assigned, a confirmation email will be sent to all site personnel.

For the Randomized Cohort, subjects will be randomized to each treatment arm (SGI-110+irinotecan or regorafenib/TAS-102) prior to treatment administration and should not exceed 1 week of the planned dose. The assignment will not be blinded. Randomization will be stratified by standard treatment (Regorafenib or TAS-102) and time from last irinotecan treatment (> 6 months or < 6 months) through a dynamic algorithm to maintain balance between the arms as much as possible. For those assigned to treatment arm with standard of care therapy will receive regorafenib (if previously received TAS-102) or TAS-102 (if previously received regorafenib). If they have never received either regorafenib or TAS-102, choice of therapy will be deferred to treating physician and patient.

This is an open-label study. There will be no blinding of treatment assignment.

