**Phase II secondary objectives:**

1. Evaluate and compare response rates between arms of the study as determined by RECIST criteria 1.1.
2. Evaluate and compare overall survival (OS) between arms of the study.
3. Assess for potential predictive markers of survival using baseline tissue.
4. To assess the pharmacokinetics of SGI-110 in metastatic colon cancer patients and correlate with changes in global methylation.

**Sample Size/Accrual Rate:** The median PFS of patients on the phase III CORRECT trial of Regorafenib in metastatic colorectal cancer reported by Grothey and Van Cutsem was 1.9 months. The median PFS of patients on the phase III RECURSE trial of TAS-102 in metastatic colorectal adenocarcinoma reported by Mayer was 2.0 months. The PFS curves of these two trials were superimposable and therefore hazard rates over four time intervals were estimated based on the published PFS curve (figure 3.) for Regorafenib from the CORRECT trial. Simple linear regressions were used to fit the natural logarithm of the Kaplan-Meier product limit estimate of the PFS function as a function of time in four intervals: from 1 to 6 weeks, 6 to 12, 12 to 18, and 18 to 56 weeks. These estimated hazard rates: 0.0113, 0.0558, 0.3238, and 0.0748 per person week were used in simulations to evaluate power for this study. We hypothesize that the SGI-110 combination treatment will improve the 4 month PFS from 23% to 46.5%. Patients will be randomized to the SGI-110 + irinotecan (Arm A) and the Regorafenib or TAS-102 arm (Arm B) in a 2:1 ratio. Using a one sided 5% type I error allowance, accrual of 48 patients per year for 2 years (Arm A and B target sample sizes of 64 and 32 respectively) with an additional 2 years of follow up, this study will provide sufficient events to have 83% power to detect an improvement of the median PFS from 1.9 months to 3.6 months, i.e. a hazard ratio of 0.526.

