The reference hazard rates were estimated based on the published PFS curve (figure 3.) for Regorafenib. Simple linear regressions were used to fit the natural logarithm of the Kaplan-Meier product limit estimate of the survival function as a function of time in four intervals: from 1 to 6 weeks, 6 to 12, 12 to 18, and 18 to 56 weeks. Survival times were then generated using a piecewise exponential distribution with these estimated hazard rates: 0.0113, 0.0558, 0.3238, and 0.0748 per person week. For simulation purposes, the effect of treatment was assumed to multiply these hazard rates by factors of 1.0 (no difference), 0.80, 0.60, 0.526, 0.50, 0.40 and 0.35. The randomization ratio for these simulated studies was 2:1 and a single interim analysis, evaluating 4 month PFS, was performed after 50% of the patients were enrolled, i.e. n=32 in Arm A (SGI-110) and n=16 in Arm B (Regorafenib or TAS-102). A one-sided 0.05 alpha level log-rank test was used for the final analysis. Plots of the reference curve (black) and six scenarios of treatment effects (red) are shown in figure 1. In scenario one, the reference and treatment hazard rates are equal. Table 1 gives operating characteristics of this monitoring plan for these scenarios. Column 4 in table 1 is the proportion of studies rejecting the null hypothesis out of the number of studies that did not stop for futility. Column 5 is the overall proportion of studies with a positive result.

Table 1. Operating characteristics of monitoring rule from 500 simulated studies with interim analysis on 4 month PFS and final analysis based on the log-rank test.

Scenario	Control hazard rate ( $\lambda$ ) multiplier	Stop for Futility %	Rejected at final analysis %*	Overall studies rejecting Ho %
1	1.00	26.4%	5.4%	4.0%
2	0.80	12.8%	22.0%	19.2%

CONFIDENTIAL

This document is confidential. Do not disclose or use except as authorized.

3	0.60	5.2%	68.8%	65.2%
4	0.526	2.0%	84.7%	83.0%
5	0.50	1.2%	89.1%	88.0%
6	0.40	0.6%	98.4%	97.8%
7	0.35	0.0%	99.8%	99.8%

\*Denominator is the number of simulations that do not stop early for futility.

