### Analysis of primary objective:

Standard life table methods will be used to analyze PFS. We will report the 4-month, 1-year and median PFS with 95% confidence intervals for both arms of the study.

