### Analysis of secondary objectives:

1. The 4-month PFS will be compared between arms of the study using a one-sided, 0.05 alpha level, log-rank test.
2. All patients included in the study must be assessed for response to treatment, even if there are major protocol treatment deviations. Each patient will be assigned one of the following categories: 1) complete response, 2) partial response, 3) stable disease, 4) progressive disease, 5) early death from malignant disease, 6) early death from toxicity, 7) early death because of other cause, or 9) unknown (not assessable, insufficient data).  
All subjects in the study will be included in the main analysis of the response rate. Patients in response categories 4-9 should be considered to have a treatment failure (disease progression). Thus, an incorrect treatment schedule or drug administration does not result in exclusion from the analysis of the response rate. Response rate will be estimated overall and by treatment arm. A Fisher's Exact or chi square test will be use to compare response rates across treatment arms.
3. Standard life table methods will be used to analyze OS. Four month, 1-year and median survival will be reported, overall and by treatment arm. We acknowledge that OS assessment will be compromised with the cross-over design and will report as such.
4. Baseline global methylation will be categorized as high or low and OS Kaplan Meier curves plotted by category. The change in global methylation will be categorized as positive or negative and OS Kaplan Meier curves plotted by category. Similar analyses will be used for individual expression markers.

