### **Stratification Factors**

Patients will be stratified by two factors: assignment to Regorafenib or TAS-102, and time from last irinotecan treatment (>6 months or < 6 months) through an algorithm to maintain balance between the arms as much as possible.

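### The between-arm PFS test uses neither randomisation factor and no hazard ratio is planned; how much power this costs depends on prognostic strength that the documents do not give

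*Combined protocol and SAP*

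**What the plan says.** **Allocation.** Section 4.3 states: "Randomization will be stratified by standard treatment (Regorafenib or TAS-102) and time from last irinotecan treatment". It does this "through a dynamic algorithm to maintain balance between the arms as much as possible", without describing the algorithm. Section 14.1, Stratification Factors, repeats the two factors ("Patients will be stratified by two factors: assignment to Regorafenib or TAS-102, and time from last irinotecan treatment") and links them to no analysis.

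**Test.** Under Futility monitoring plan, the account of the design simulations says: "A one-sided 0.05 alpha level log-rank test was used for the final analysis". The instruction for the trial itself is item 1 under Analysis of secondary objectives: "The 4-month PFS will be compared between arms of the study using a one-sided, 0.05 alpha level, log-rank test". Neither sentence mentions strata or covariates.

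**Estimation.** The whole between-arm content of Analysis of primary objective would have to come from this sentence: "We will report the 4-month, 1-year and median PFS with 95% confidence intervals for both arms of the study". It describes each arm separately. No hazard ratio, Cox model or difference between arms appears anywhere in the analysis text.

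**Objective.** Section 14.1 defines the primary objective as a comparison of PFS between the arms. The Sample Size/Accrual Rate paragraph powers it at 83% for a hazard ratio of 0.526, with 64 and 32 patients and a one-sided 5% error rate.

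**The concern.** A factor is normally balanced at randomisation because it is expected to predict outcome. If it does, a log-rank test that ignores it treats the variation between strata as noise. The test statistic is then too small on average, and the unadjusted hazard ratio moves toward 1. The irinotecan interval is the factor to consider first, because the trial's hypothesis is sensitisation to irinotecan retreatment.

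The design simulations draw all control patients from one curve, so the stated power does not show whether the choice matters.

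The missing effect estimate is a separate gap and depends on no assumption. A comparison designed on a hazard ratio would end with a p-value filed under secondary objectives and two sets of per-arm figures.

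**Working it through.** **Inputs from Section 14.1.** 64 and 32 patients; one-sided 0.05; hazard ratio 0.526; control hazards 0.0113, 0.0558, 0.3238 and 0.0748 per week; 2 years of accrual plus 2 years of follow-up, so nearly all 96 patients have an event.

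**Assumed, because the documents give nothing.** Prognostic hazard ratios from 1 to 3 for each factor, with half the patients in each category.

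**Step 1: the plan's own figure.** Schoenfeld's formula is power = Φ(|ln HR| × √(d × p(1−p)) − z). With d = 96 and p = 1/3, √(96 × 2/9) = 4.619. With |ln 0.526| = 0.642, the product is 2.967.
- One-sided 0.05: Φ(2.967 − 1.645) = Φ(1.322) = 90.7%.
- Two-sided 0.05: Φ(2.967 − 1.960) = Φ(1.007) = 84.3%.

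Simulation with the stated hazards gives 90.5% without the futility look. With an approximated look it gives 88.1% overall at one-sided 0.05 and 82.2% at two-sided 0.05. The stated 83% is therefore not reproduced at the stated one-sided level. That is a separate matter: the steps below compare tests under identical conditions and do not rest on the 83%.

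**Step 2: no strata against four strata.** Stated hazards, 2:1 minimisation, no futility look, 40,000 runs per row. The first column gives the prognostic hazard ratio for control drug / irinotecan interval.

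| Prognostic HR | Null rejection, unstratified | Null rejection, four-cell | Power, unstratified | Power, four-cell | Gain (points) |
|---|---|---|---|---|---|
| 1 / 1 | 5.8% | 5.9% | 90.5% | 87.7% | −2.8 |
| 1 / 1.5 | 5.6% | 5.8% | 89.3% | 87.7% | −1.6 |
| 1.5 / 1.5 | 5.3% | 5.8% | 87.7% | 87.8% | +0.1 |
| 1 / 2 | 5.1% | 5.8% | 86.6% | 87.9% | +1.3 |
| 2 / 2 | 4.3% | 5.7% | 83.0% | 88.0% | +5.0 |
| 3 / 3 | 3.2% | 5.7% | 72.3% | 87.4% | +15.1 |

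The unstratified null rate falls as the factors become stronger. The 5.8% in the first row arises with no prognostic factor at all. It comes from the normal approximation at 64:32, and stratifying leaves it at 5.7-5.9%.

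**Step 3: stratifying on the irinotecan interval only.** Control drug is not prognostic; 2:1 blocks within strata; no futility look. Power is unstratified against stratified.

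| Interval HR | All events observed, 12,000 runs | Stated hazards, 5,000 runs |
|---|---|---|
| 1 | 90.9% vs 89.9% | 89.7% vs 88.9% |
| 1.5 | 88.9% vs 89.6% | 89.2% vs 89.7% |
| 2 | 86.4% vs 89.4% | 87.2% vs 90.5% |
| 2.5 | 83.4% vs 89.2% | not run |

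The Monte Carlo standard error of a single entry is about 0.3 points for 12,000 runs and 0.4 points for 5,000.

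**Step 4: Cox model with both factors.** In 6,000 runs per scenario, power is about 90% throughout and null rejection is 5.2-6.2%. The median unadjusted hazard ratio moves from 0.52 (no effect) to 0.55 (1 / 2), 0.57 (2 / 2) and 0.62 (3 / 3). The adjusted one stays near 0.52.

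**Step 5: unequal categories.** If only 20% of patients are in the higher-risk interval category, with interval hazard ratio 2, power is 88.1% unstratified and 87.6% with four cells. At 35% it is 87.3% and 87.9%. The gain shrinks when one category is rare.

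**The case against.** A reader might infer that the planned test certainly loses power and has the wrong error rate because it ignores the factors. The documents do not support that.

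- **Power.** No prognostic strength is reported for either factor. For control drug, the Sample Size/Accrual Rate paragraph treats the PFS curves of the two drugs' trials as coinciding, which points to little effect. With no effect, or with 1.5 on the interval alone, the planned test has more power than a four-cell stratified one.
- **Error rate.** Ignoring prognostic factors lowers the null rejection rate. The excess over 5% comes from the 64:32 approximation and is not cured by stratifying. These figures also omit the futility look; the plan's Table 1 reports 4.0% overall null rejection in 500 simulations.
- **Text.** The sentence about the final analysis describes simulations. The trial's own instruction is item 1 of the secondary analyses, which is silent on strata. Reading it as unstratified is a reasonable inference, not a stated fact.
- **Intervals.** The 95% intervals describe each arm and do not conflict with a one-sided 5% test.

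All of this stands. It removes any certain loss and the case for automatic four-cell stratification. It does not touch the two gaps: the factors used to randomise are absent from the analysis, and the comparison has no planned effect estimate. It also does not count against stratifying on the interval alone, which costs about 1 point at worst in Step 3.

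**Conclusion.** The point holds in a conditional form. It is certain from the text that the between-arm PFS test names neither randomisation factor, that it sits under secondary objectives, and that no hazard ratio or other between-arm PFS estimate is planned.

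The cost in power is conditional. Under the assumed prognostic hazard ratio of 2 on the interval alone, the planned test gives up about 3 points to one stratified on the interval. With 2 on both factors it gives up about 5 points to four-cell stratification. With no prognostic effect it gives up nothing. These sizes rest on equal categories, near-complete events and no futility look.

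The matter is worth correcting before analysis because the change is cheap. It does not threaten control of false positives.

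**What to change.** 1. In Analysis of primary objective, name the deciding PFS test: a one-sided 0.05 log-rank stratified by time since last irinotecan, using the value entered at allocation. A Cox model with both factors is an acceptable alternative. Choose one in advance, with no switch that depends on observed stratum counts. Align item 1 of the secondary analyses with it.
2. Report the hazard ratio from the matching Cox model with a 90% confidence interval, which corresponds to a one-sided 5% test. The per-arm 95% intervals can stay.
3. Assign an interval of exactly 6 months to a category; Section 4.3 and Stratification Factors leave it in neither. If control drug enters the analysis, record the intended drug for every patient before randomisation. Section 4.3 describes the choice only for patients assigned to standard care.
4. Optionally, obtain the p-value by permutation within strata or by re-randomisation, to deal with the 64:32 approximation. Re-randomisation requires the allocation algorithm to be written down.

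**Cost.** Wording in the analysis plan, a re-run of the operating-characteristics table with the chosen test, and about 1 point of power if the interval turns out not to be prognostic.
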